Genotropin
Special Investigation
– SGA long-term follow-up investigation –

Protocol

SGA (small-for-gestational age) dwarfism
without epiphyseal closure

Pfizer Japan Inc.

Date prepared: July 2, 2013 (Ver. 2)

[figure not shown]
Protocol No.: A6281314

Ver.2

Summary

Genotropin Special Investigation - SGA long-term follow-up investigation - is a post-marketing database of children receiving Genotropin for the treatment of SGA (small-for-gestational age) dwarfism without epiphyseal closure. The outcome of this database is intended for public release at academic conferences and in scientific journals, and to contribute to the growth hormone treatment of patients with SGA dwarfism.

Introduction

Genotropin Special Investigation - SGA long-term follow-up investigation - (hereinafter, this investigation) is an investigation intended to evaluate the long-term efficacy and safety of Genotropin in children with SGA dwarfism without epiphyseal closure. This investigation will be commenced upon consent of each relevant patient to receive a long-term Genotropin therapy.

The information collected in this investigation will be used to provide proper drug use and as part of safety information to be provided. Therefore, this investigation must be conducted with "Good Post-Marketing Study Practice" [Ministry of Health, Labour and Welfare (MHLW) Ordinance No. 171, December 20, 2004].

Data obtained from the patients enrolled in this investigation will be reported to regulatory authorities pursuant to the Pharmaceutical Affairs Law. Also, the data reported to regulatory authorities may be publicly posted in MHLW's "Pharmaceuticals and Medical Devices Safety Information" and "Pharmaceuticals and Medical Devices Information Website (<http://www.info.pmda.go.jp>)" as a listing of patients, which will present the names of drugs, adverse reactions, gender, age (increment of 10 years), and other relevant information. Furthermore, the data collected may also be disclosed if the MHLW is inquired to disclose such data in accordance with "Act on Access to Information Held by Administrative Organs" (Law No. 42 of May 14, 1999); provided that in no event will the names of investigators, hospitals and other personal information be made subject to such reporting, nor will it be posted or disclosed in any form or shape.

Meanwhile, the data collected from this investigation shall be anonymized, compiled, and used as evidence for mechanisms and causes of poor physical growth in children with SGA dwarfism without epiphyseal closure, as well as response of such children to growth hormone treatment, and to facilitate new findings and discovery concerning poor physical growth in children.

1. Objective

This investigation is intended to evaluate the long-term efficacy and safety of Genotropin in children with SGA dwarfism without epiphyseal closure. Responses of patients to Genotropin in relation to clinical conditions of patients, dose schedule, past history of growth hormone treatment, and other relevant factors will be investigated.

2. Study subjects

The indication for Genotropin in this investigation is as follows.

<Indication>

SGA (small-for-gestational age) dwarfism without epiphyseal closure

Subjects with the above disease who meet the following conditions will be enrolled in this investigation. In addition, the data in patients receiving Genotropin prior to the contract conclusion will also be included in this investigation.

- [1] Patients receiving Genotropin and consenting in writing to take part in this investigation
- [2] Newly enrolled patients who meet the following enrollment criteria
- [3] Patients who have already been enrolled in "Genotropin Special Investigation - Investigation of Genotropin long-term use in patients with SGA dwarfism without epiphyseal closure."

<Enrollment criteria>

Patients who meet all of the following criteria

- 1) Patients whose height and weight at birth are both below the 10th percentile for patients of the same gestational age, and at the same time, either body weight or height is less than -2 SD compared to patients of the same gestational age. Neonates whose body height at birth were immeasurable and thus were not measured will be evaluated with birth weight.
- 2) Eligibility for the treatment
 - [1] Patients must be not younger than 3 years.
 - [2] The current body height must be less than -2.5 SD of the standard height.
 - [3] A pre-treatment height velocity within 1 year prior to the commencement of treatment must be less than 0 SD.
- 3) Patients whose poor physical growth after birth is attributable to disease other than intrauterine growth retardation cannot be enrolled in this investigation. Also patients who are currently receiving treatment that is known to cause poor physical growth cannot take part in this investigation.

3. Target sample size

The target number of subjects from which data will be collected is 400.

Ver.2

4. Duration of investigation

The duration will be from April 2013 to March 2016 (3 years); provided that it may be extended depending on the progress of the investigation.

The investigation will be continued as long as the subject is receiving Genotropin, or as determined appropriate by the investigator.

5. Investigation procedures

5.1. Investigation method

This is a multicenter open-label investigation to which subjects are enrolled with a central registration method.

5.2. Data collection method

In this investigation, data will be collected with case report/verification forms provided by Pfizer Japan, Inc. (hereinafter, "Sponsor"). Upon completion of the assessment period and height follow-up period, each investigator shall promptly complete the report/verification forms, and submit them to Sponsor.

5.3. Patient registration

Newly enrolled patients and ongoing patients*¹ will be included in this investigation. Before the commencement of investigation in each patient, the investigator shall obtain an informed consent of the patient or his/her parent (or a legally acceptable representative) in writing to take part in this investigation. If the subject meets all the enrollment criteria, the investigator shall complete the enrollment form with the name of sites, department, and attending doctor, ID number, patient's initials (not essential), gender, date of birth, and the status of informed consent.

5.3.1. Enrollment of new subjects

For the enrollment of a new subject, the investigator will, in addition to above information, complete an "Enrollment Form for New Subject" provided by Sponsor, in which, the date Genotropin therapy was commenced, the date the initial growth hormone therapy was commenced, and the eligibility to take part in this investigation should be recorded, and submitted to Sponsor. Subjects who have commenced on Genotropin therapy prior to the contract conclusion should be enrolled in this investigation promptly upon the contract conclusion.

5.3.2. Enrollment of ongoing patients*¹

"Enrollment Form for Ongoing Subject" should be completed and submitted to Sponsor for all patients who are transferring from "Genotropin Special Investigation - Investigation of Genotropin long-term use in patients with SGA dwarfism without epiphyseal closure."

*¹: Ongoing subjects are defined as patients in whom data was collected in "Genotropin Special Investigation - Investigation of Genotropin long-term use in patients with SGA dwarfism without epiphyseal closure."

Ver.2

5.3.3 Data to be provided to the Foundation for Growth Science in Japan

Investigator may provide the data recorded in the report forms to the Foundation for Growth Science in Japan; provided that the investigator is required to obtain consent of the patient or his/her parent (or a legally acceptable representative) for sharing such data with the foundation, and checkmark the relevant section concerning such consent in the enrollment form, and submit it to Sponsor.

5.4. Assessment period

5.4.1. Assessment period for newly-enrolled subjects

The fiscal assessment period of the year in which subject is enrolled will be defined as a period starting with the commencement of Genotropin therapy (which may be tracked back) and ending with the fiscal end. The fiscal assessment period of each subsequent year will be defined as the corresponding annual fiscal period.

5.4.2. Assessment period for ongoing subjects

For patients transferring from "Genotropin Special Investigation - Investigation of Genotropin long-term use in patients with SGA dwarfism without epiphyseal closure," the initial fiscal assessment period will be defined as a period starting on the day following the final assessment of data recorded in the last booklet for "Genotropin Special Investigation - Investigation of Genotropin long-term use in patients with SGA dwarfism without epiphyseal closure" and ending with the fiscal end of the applicable year. The fiscal assessment period of each subsequent year will be defined as the corresponding annual fiscal period.

5.4.3 Height follow-up period

Patients completing or discontinuing Genotropin therapy will be followed up to document body heights from the completion or discontinuation of Genotropin therapy to the completion of investigation or until reaching adult height (final assessment). The follow-up period for each booklet will correspond to each fiscal year.

Note: "The date of final assessment" in each booklet of case report will be the date of final assessment in the corresponding fiscal year.

Note: The completion of treatment is defined as the completion of Genotropin therapy for the therapeutic objective initially intended at the commencement of treatment being judged as cured etc.

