5.6. Notes concerning completion, correction, and reviewing of report/verification forms

(1) Completion procedures

Investigator will, upon confirming the survey items, complete the report/verification forms with data based on medical record including laboratory data; a pen, ballpoint pen, or other inerasable means should be used to complete the forms. The data after the completion of Genotropin therapy may be collected through telephone or other verbal means.

(2) Data correction

Any corrections on the report to be made by the investigator will be struck out with a double line so that the original description can be legible, and put on a "correction seal". Upon receiving Sponsor's inquiry on the content of report form, the investigator will review the medical record described earlier, and as required, correct relevant sections and resubmit the forms.

(3) Data verification

Upon completion of all entries and corrections in the report/verification forms, the investigator will once again review the information on the forms and associated query forms, and sign or seal/name the relevant sections on the forms.

(4) Submission of report forms

Investigators must prepare a report/verification form and submit it to Sponsor promptly upon the completion of the assessment period and height follow-up period.

Ver.2

6. Assessment variables and time points

Investigator will conduct this investigation in accordance with the following assessment schedule. After the contract is concluded, the investigator shall enroll patients who meet the eligibility criteria, and complete the report/verification form upon confirming the baseline patient characteristics and other relevant data. The data will be collected from the birth of the subject to the completion of investigation (which will be determined by the subject, his/her parent [or a legally acceptable representative], or the attending doctor).

[Assessment schedule]

	Enrollment Form for New Subject	Newly-enrolled subjects Report forms (Booklet 01)	Enrollment Form for Ongoing Subject	Report forms (Booklet 02) Follow up	Height Follow-up Form*
Assessment variables and time points	Enrollment	Assessment period	Enrollment	Assessment period	Height follow-up period
		From commencement of treatment to the fiscal end of the enrollment year		Until the end of the fiscal year**	From completion/discontinuation of treatment to each fiscal end
Patient identification	Identification number	●	●(Copy)	●	●

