6.8. Height follow-up after completion or discontinuation of Genotropin therapy

"Height Follow-up Form" will be used to collect data concerning body height in patients completing or discontinuing Genotropin therapy, and meeting the following criteria.

- Patients not switching to other drug product
- Patients not reaching adult height (final height)

[1] Date on which height follow-up is completed

[2] Height (to the first decimal place), and weight (to the first decimal place)

[3] Bone age

[4] Pubescence

[5] Future treatment strategy

Note: Any occurrence of adverse event during the height follow-up period should be separately investigated in details as determined necessary by Sponsor.

7. Analysis plan

Statistical analysis on safety and efficacy shall be performed; the results of which shall be posted in scientific journal, and reported at academic conferences and through research activities. In no event shall the investigator inquire Sponsor to perform statistical analysis for this investigation without confirming with Japan Genotropin Advisory Board in advance.

8. Discontinuation

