5.3. Other Analysis Sets

Set of patients who reached adult height (near final height).

The set of patients who reached adult height (near final height) is defined as a set of patients in the efficacy analysis set for whom adult height (near final height) was measured. Adult height (near final height) is defined as height after the time point that any of the following conditions is met.

- a. Annual height velocity of less than 2 cm after the maximum growth by puberty.¹
- b. Bone age of 17 years or older for males and 15 years or older for females.¹
- c. Reason for discontinuation in patient's profile of "reaching adult height (near final height)" or "epiphyseal closure".

Set of patients who did not reach adult height (near final height).

The set of patients who did not reach adult height (near final height) is defined as a set of patients in the efficacy analysis set who meet all the following conditions at the discontinuation of treatment and for whom height was measured at least once on Day 91 after the discontinuation of treatment or later.

- a. No puberty.
- b. Annual height velocity of 2 cm or higher after the maximum growth by puberty.
- c. Bone age of less than 17 years for males and less than 15 years for females.
- d. Reason for discontinuation in patient's profile of "reaching the standard height," "growth rate," "preference of patient/parent(s)," "non-compliance," "discontinuation of public funding," "change in diagnosis," "poor clinical response," "adverse event," "laboratory abnormal," or "others".

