6.2. Efficacy Endpoints

- Height.
- Height SDS: $(\text{height} - \text{standard height for chronological age/gender}^2) / \text{standard deviation}$.
- Height velocity: $365.25 \times (\text{height} - \text{height of 1 year before}) / (\text{date of height measurement} - \text{date of height measurement of 1 year before})$ (height of 1 year before: Height of the previous year as used according to “[Appendix A1.3](#) Definition of timing for visit 3”).
- Height velocity SDS: $(\text{height velocity} - \text{mean height velocity for chronological age/gender}^3) / \text{standard deviation}$.

CCI

- [REDACTED]
- [REDACTED]
- [REDACTED]

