7. HANDLING OF MISSING VALUES

Any missing data on the seriousness, measures taken, and outcome of adverse events will be handled as “unknown” in summarizing data.

Measured values outside the acceptable range (Appendix 1) at each evaluation time point of the efficacy endpoints and clinical laboratory parameters will be handled as missing and missing data will not be imputed.

The procedure to handle uncleaned data is described below.

- Items with missing data: Missing data will be handled as missing (“unknown” for the category of classification variables) for both tabulation and listing.
- Items with inconsistent data: Inconsistent data will be handled as missing for both tabulation and listing. In this regard, however, a data handling list will be prepared separately.
- No signature: Descriptions in the report form without signature of the contract physician (or with signatures of other physicians than the contract physician) will be handled as missing for both tabulation and listing. No date or inconsistent date in the signature date section (eg, date of signature before or after the start date of treatment) will be considered to indicate that there is no signature on the report form.

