11. APPENDIXES

11.1. Appendix 1: Details of Data Extraction

A1.1 DEFINITION OF TIMING FOR VISIT 1

Timing for visit	Endpoint	Definition [allowable range]
3 years	Height Height SDS Body weight SDS BMI SDS IGF-I SDS	3 years and 0 month to 3 years and 11 months
4 years	Height Height SDS Body weight SDS BMI SDS IGF-I SDS	4 years and 0 month to 4 years and 11 months
N years	Height Height SDS Body weight SDS BMI SDS IGF-I SDS	N years and 0 month to N years and 11 months

The measured value on the latest date will be used when the same patient receives more than one measurement during the same visit.

A1.2 DEFINITION OF TIMING FOR VISIT 2

Timing for visit	Endpoint	Definition [allowable range]
Start of Genotropin therapy	Height SDS Body weight SDS BMI SDS IGF-I SDS	90 days before the first date of treatment (the start date of treatment) to the start date of treatment for this investigation
Pubescence	Height SDS Body weight SDS BMI SDS IGF-I SDS	The date evaluated as the pubescence +90 days
At reaching adult height (near final height)	Height SDS Body weight SDS BMI SDS IGF-I SDS	The date evaluated to reach adult height (near final height) +90 days

The measured value on the earliest date will be used when the same patient receives more than one measurement during the same visit.

In this regard, all the data measured after reaching adult height (near final height) will be used if plots are prepared.

A1.3 DEFINITION OF TIMING FOR VISIT 3

Timing for visit	Endpoint	Definition [allowable range]
Start of Genotropin therapy	Laboratory test parameters Height SDS Height velocity Height velocity SDS Body weight SDS BMI SDS IGF-I SDS	90 days before the first date of treatment (the start date of treatment) to the start date of treatment for this investigation
1 year later	Laboratory test parameters Height SDS Height velocity Height velocity SDS Body weight SDS BMI SDS IGF-I SDS	365 ±90 days after the start of treatment
2 years later	Laboratory test parameters Height SDS Height velocity Height velocity SDS Body weight SDS BMI SDS IGF-I SDS	730 ±90 days after the start of treatment
N years later	Laboratory test parameters Height SDS Height velocity Height velocity SDS Body weight SDS BMI SDS IGF-I SDS	365 × N ±90 days after the start of treatment
Completion of Genotropin therapy	Laboratory test parameters Height SDS Height velocity Height velocity SDS Body weight SDS BMI SDS IGF-I SDS	Final date of treatment for this investigation (completion date of treatment) ±90 days

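### Post-treatment heights come on fiscal-year forms, but the SAP's yearly change rows and height velocity accept them only near the treatment anniversary, so up to half of the yearly values, and more of the velocities, may be missing

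*Protocol*

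**What the plan says.** **Collection.** Children who complete or stop Genotropin, have not reached adult height and have not switched product are followed on the Height Follow-up Form. Protocol 5.4.3 says: "The follow-up period for each booklet will correspond to each fiscal year". The assessment schedule in Protocol section 6 gives the form's period as "From completion/discontinuation of treatment to each fiscal end". Section 6.8 lists the form's items: a date ("Date on which height follow-up is completed"), height and weight, bone age, pubescence and the future treatment strategy. It gives neither a measurement date nor a number of readings per form.

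**Analysis.** SAP Appendix A1.3 defines the yearly rows as "365 × N ±90 days after the start of treatment". It adds a row for the end of treatment, "Final date of treatment for this investigation (completion date of treatment) ±90 days", and one for the completion of height follow-up, also ±90 days. SAP section 7 treats as missing, without imputation, "Measured values outside the acceptable range (Appendix 1) at each evaluation time point". SAP 6.2 defines height velocity with an earlier height described as "Height of the previous year as used according to" A1.3.

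**Where this is used.** SAP 8.2.4.2 to 8.2.4.4 summarise change from start, with a 95% confidence interval, at the A1.3 time points, including in the set that did not reach adult height. SAP 5.3 counts adult height as reached on any one of three conditions: a is "Annual height velocity of less than 2 cm after the maximum growth by puberty", b is a bone-age threshold, and c is the recorded reason for discontinuation.

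**The concern.** The forms follow the fiscal calendar and the yearly rows follow each child's own start date, and nothing connects the two. If a child is measured once per fiscal year at about the same time, the distance from the treatment anniversary stays nearly constant. That child then tends to fall inside the window every year or outside it every year.

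Velocity is hit harder, because it needs an A1.3 height in the previous year as well as the current one. A1.1, the by-age scheme, has no velocity row, so it cannot fill the gap. Two things are at stake: the yearly off-treatment change in height SDS and in velocity, and adult-height condition 5.3 a for children who stopped treatment before reaching adult height.

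**Working it through.** The documents give no missingness rate for this point, so there is no figure of theirs to reproduce.

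**Inputs from the documents.** Yearly window 365 × N ±90 days (SAP A1.3); one form per fiscal year (Protocol 5.4.3); velocity needs the previous-year A1.3 height (SAP 6.2).

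**Assumptions, not in the documents.** Start dates are uniform over the year. The number of heights per form is one or two. Reading dates are either the same each year or independent from year to year.

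**1. Yearly value, one height per fiscal year.** Window length = 2 × 90 + 1 = 181 days. Share inside = 181/365 = 49.6%; share outside = 184/365 = 50.4%.

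**2. Yearly value, two heights six months apart.** Share with at least one inside = 181/182.5 = 99.2%, so about 1% are lost.

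**3. A given pair of consecutive yearly follow-up heights (needed for velocity), one height per fiscal year.**
- Same date each year: both are inside or both outside, so unavailable = 184/365 = 50.4%.
- Readings in the last 90 days of each fiscal year: mean gap between two such dates = 90/3 = 30 days; both inside = (181 − 30)/365 = 41%; unavailable = 59%.
- Independent dates: unavailable = 1 − (181/365)² = 75.4%.

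If the earlier height is an on-treatment reading that is always in its window, only the later one matters and 50.4% are unavailable.

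**4. Children with no follow-up height in any yearly row.** Same date each year: about 50%, however long the follow-up. Independent dates: (184/365)^K for K years, which gives 50%, 25%, 13% and 6% for K = 1 to 4.

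**5. Adding the other two A1.3 rows.** If follow-up is completed on the date of the last height, every child keeps at least one A1.3 value, so 0% lose all. If completion is taken as the fiscal year end, a simulation of 400,000 children with uniform start, stop and reading dates leaves about 36% with none (same date each year), or 36% falling to 5% over one to four years (independent dates).

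**6. By-age summaries.** A1.1 covers whole age-years without a gap, so the window loses no height or height SDS there, although only the latest value in each age-year is used.

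**The case against.** A reader might infer that the SAP accepts follow-up heights only near the anniversary, so that about half of followed children lose every follow-up height. The documents do not support that. Section 7 makes a value missing at an evaluation time point; it does not delete the measurement. A1.1 keeps height and height SDS by age for the efficacy, eligible-criteria, reached and not-reached sets. The completion-of-follow-up row is not tied to the anniversary. The individual plots continue after treatment. Membership of the not-reached set, as far as timing goes, needs only a height on Day 91 or later after stopping.

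The figure of one half is also conditional. Section 6.8 lists items, not the number of readings, and Appendix 1 provides for several measurements in one visit. Nothing fixes the reading to the same date each year. Adult height can be met through bone age, which the form collects, and 5.3 does not cite 6.2 for its velocity. The analysis is exploratory, with no decision rule (SAP 4.1, 4.2).

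All of this limits the point but does not remove it:
- A1.1 supplies neither velocity nor change from start with its confidence interval.
- The end-of-treatment row stops at day +90, just before the Day 91 heights that qualify a child for the not-reached set.
- The completion row can keep a height, but its velocity still needs a previous-year A1.3 height, which may be absent.
- Varying reading dates make a lost pair more likely, not less.
- SAP 6.2 is the only definition of post-baseline velocity, so it is the natural reading of 5.3 a.
- Bone age helps only if it is taken, and Protocol 5.6 allows post-treatment data to be collected by telephone.
- Condition 5.3 c rarely helps, because children already at adult height do not use this form.

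**Conclusion.** The mismatch is real and confined to the A1.3 yearly rows and to velocity. With one height per fiscal year and uniform start dates, about 50% of yearly A1.3 follow-up values are missing. A given consecutive pair of follow-up heights is unavailable for velocity in about 50% (same date each year) to 75% (independent dates). With two heights six months apart, about 1% of yearly values are lost. The sponsor can settle where the truth lies by looking at its own form.

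The effect on adult height is partial. If 5.3 a uses the velocity of 6.2, it cannot be tested for some followed children. How many would still be recognised through bone age cannot be computed from the documents, so no net under-count is claimed. The point deserves correction because the loss is avoidable and depends on the calendar, but it does not threaten the by-age results.

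**What to change.** In SAP 6.2, for measurements after the last dose, define annual velocity from two recorded heights 365 ±90 days apart by their actual dates, wherever they fall relative to the treatment anniversary. Say whether the earlier height may precede the last dose and which one is used if several qualify. Apply the definition to the completion-of-height-follow-up row, and state in 5.3 a that it is the velocity meant.

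With one height per year on the same date, or always within the last 90 days of the fiscal year, every consecutive pair then qualifies. With fully independent dates the share rises from (181/365)² = 25% to about 1 − (1 − 90/365)² = 43%, so the recovery is not complete in that case.

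Optionally, as a sensitivity summary, assign follow-up height SDS and weight SDS to the nearest year by actual date. Widening the main A1.3 windows is not needed.

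The cost is SAP wording and a little programming, with no new data. Follow-up values would sit slightly less tightly around the anniversary. The interval behind each velocity would be 275 to 455 days, against the 185 to 545 days (365 ± 180) that two adjacent A1.3 windows already permit.
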